2.2. Background

LY3435151 is a fully human immunoglobulin-G1 antibody with Fc effector-null mutations, targeting the CD226 receptor. The activity of LY3435151 has been tested and confirmed in a variety of biological assays, including in vitro T cell functional assays. In tumor models with humanized mice, LY3435151 has shown similar to superior antitumor efficacy compared to anti-PD-L1 monotherapy.

The biological properties of antibody LY3435151 were characterized both in vitro and in vivo in nonclinical pharmacology studies, as described as follows:

- Binds human and cynomolgus monkey CD226 proteins with similar affinity
- Demonstrates no apparent binding to Fcγ receptors or immune effector function
- Displays agonist functional activity and stimulates T cell activation in vitro
- Demonstrates no apparent platelet activation in vitro
- Shows potent antitumor efficacy in humanized mouse models in vivo

As detailed in the Investigator's Brochure (IB), overall preclinical safety data support the proposed LY3435151 starting dose and dose escalation design of Study JZIA. Further details regarding the dosing rationale of LY3435151 for Study JZIA with supporting preclinical data may be found in Section 4.3.

Refer to the IB for detailed information pertaining to nonclinical efficacy, safety, and pharmacokinetics (PK).

Pembrolizumab is a potent humanized immunoglobulin G4 (IgG4) monoclonal antibody (mAb) with high specificity of binding to the PD-1 receptor, thus inhibiting its interaction with PD-L1 and programmed cell death ligand 2 (PD-L2). Based on preclinical in vitro data, pembrolizumab has high affinity and potent receptor blocking activity for PD-1. Pembrolizumab has an acceptable preclinical safety profile and is in clinical development as an intravenous (IV) immunotherapy for advanced malignancies. Keytruda® (pembrolizumab) is indicated for the treatment of patients across a number of indications. For more details on specific indications

refer to the IB. Refer to the IB/approved labeling for detailed background information on MK-3475.

Therapeutic studies in mouse models have shown that administration of antibodies blocking PD-1/PD-L1 interaction enhances infiltration of tumor-specific CD8+ T cells and ultimately leads to tumor rejection, either as a monotherapy or in combination with other treatment modalities (Strome et al. 2003; Blank et al. 2004; Hirano 2005; Curran 2010; Pilon et al. 2010; Weber 2010; Spranger 2014). Anti-mouse PD-1 or anti-mouse PD-L1 antibodies have demonstrated antitumor responses in models of squamous cell carcinoma, pancreatic carcinoma, melanoma, acute myeloid leukemia and colorectal carcinoma (Strome et al. 2003; Zhang et al. 2004; Nomi et al. 2007; Curran et al. 2010; Pilon et al. 2010). In such studies, tumor infiltration by CD8+ T cells and increased IFN- γ , granzyme B and perforin expression were observed, indicating that the mechanism underlying the antitumor activity of PD-1 checkpoint inhibition involved local infiltration and activation of effector T cell function in vivo (Curran 2010). Experiments have confirmed the in vivo efficacy of anti-mouse PD-1 antibody as a monotherapy, as well as in combination with chemotherapy, in syngeneic mouse tumor models (see the IB).

2.3. Benefit/Risk Assessment

More information about the known and expected benefits, risks, serious adverse events (SAEs), and reasonably anticipated adverse events (AEs) of LY3435151 are to be found in the IB.

Pembrolizumab is a PD-1 blocking antibody with global regulatory approvals in several indications (Keytruda USPI and SPC). The risk profile of pembrolizumab is well characterized, and the management of immune-related adverse events (irAEs) associated with pembrolizumab is part of national guidelines and clearly described in this protocol.

Section 2.1 provides the rationale for the expected benefit, supporting the investigation of LY3435151 in combination with pembrolizumab. Pre-clinical data suggest that some of PD-1 signaling works through cross-talk with the CD226 signaling pathway. Therefore, the benefit of combining CD226 agonist with PD-1 blockade may be stronger activation of tumor-specific cytotoxic T-cells. This would potentially create better anti-tumor immune responses with combination therapy compared to anti-PD-1 blockade alone. Likewise, the same mechanism has the potential to make toxicities, such as irAEs, more frequent or more severe.

3. Objectives and Endpoints

Objectives	Endpoints
Primary	

 • Ph1a Dose Escalation (Part A & Part B): To assess the safety and tolerability of LY3435151, thereby identifying the RP2D, administered as monotherapy and in combination with pembrolizumab, in patients with advanced solid tumors of the following types: TNBC, gastric adenocarcinoma, HNSCC, squamous cervical carcinoma, high grade serous ovarian carcinoma, HCC, UPS, and LMS. 	
 • DLTs • Safety (including, but not limited to): TEAEs, SAEs, deaths, and clinical laboratory abnormalities per CTCAE (version 5.0)

 • Ph1b Dose Expansion (Part C & Part D): To assess the safety and tolerability of LY3435151: 
 ○ administered as monotherapy (Part C), all patients must be PD-1/PD-L1 antagonist naïve: 
 C1: TNBC(not eligible for IO therapies) C2: gastric adenocarcinoma ○ administered in combination with pembrolizumab (Part D), all patients must be PD-1/PD-L1 antagonist naïve: 
 D1: TNBC (not eligible for IO therapies) D2: Gastric adenocarcinoma D3: TIL selected cohort with the following tumor types: HNSCC, squamous cervical carcinoma, high grade serous ovarian carcinoma, HCC, UPS, and LMS. 	
 • Safety endpoints, including but not limited to the following: 
 ○ TEAEs, SAEs • Clinical laboratory tests, vital signs, and physical examinations

Secondary	

 To assess the PK of LY3435151, administered as monotherapy and in combination with pembrolizumab, in patients with solid tumors 	
 Serum concentration of LY3435151 alone and when administered in combination with pembrolizumab

 To document any antitumor activity per RECIST v1.1 observed with LY3435151, when administered as monotherapy or in combination with pembrolizumab, in patients with solid tumors 	
 ORR DCR DoR TTR PFS
Tertiary/Exploratory	

 To assess the relationship between biomarkers, dose/exposure, and clinical outcomes, particularly in relation to tumor TIL levels 	
 Results of biomarker assessments Clinical outcomes data

 To document any antitumor activity per RECIST v1.1 observed with LY3435151 when administered as monotherapy or in combination with pembrolizumab to patients with solid tumors associated with TIL positivity 	
 OS

 To document antitumor activity based on iRECIST observed with LY3435151 when administered as monotherapy or in combination with pembrolizumab to patients with solid tumors associated with high TIL positivity. 	
 iORR iPFS iDoR

Abbreviations: CTCAE = Common Terminology Criteria for Adverse Events; DCR = disease control rate; DLT = dose-limiting toxicity; DoR = duration of response; HCC = hepatocellular carcinoma; HNSCC = head and neck squamous cell carcinoma; iDoR = duration of response per iRECIST; IO = immuno-oncology; iORR = overall response rate per iRECIST; iPFS = progression-free survival per iRECIST; iRECIST= immuno-Response Criteria in Solid Tumors; LMS = leiomyosarcoma; ORR = overall response rate; OS = overall survival; Ph = Phase; PFS = progression-free survival; PK = pharmacokinetics; RECIST = Response Criteria in Solid Tumors; RP2D = recommended phase 2 dose; SAE = serious adverse event; TEAE = treatment-emergent adverse event; TIL = tumor-infiltrating lymphocyte; TNBC = triple-negative breast cancer; TTR = time to response; UPS = undifferentiated pleomorphic sarcoma.

4. Study Design

4.1. Overall Design

Study JZIA is a Phase 1a/1b, multicenter, open-label dose-escalation study followed by a randomized dose-expansion study of LY3435151 as monotherapy and in combination with pembrolizumab in patients with advanced solid tumors.

Section 1.2.1 contains the study schema for Phase 1a and Section 1.2.2 contains the study schema for Phase 1b.

4.1.1. Dose Escalation Phase

Phase 1a (dose escalation) will assess the safety and tolerability of LY3435151 to identify a monotherapy recommended phase 2 dose (RP2D) and a combination RP2D in patients with solid tumors associated with TIL positivity:

- TNBC
- Gastric adenocarcinoma (including gastroesophageal junction)
- HNSCC
- Squamous cervical carcinoma
- High-grade serous ovarian carcinoma
- HCC
- UPS and LMS.

Patients enrolled in Part A (Cohorts A1 through A6) will receive LY3435151 monotherapy. Patients enrolled in Part B (Cohorts B1 and B2) will receive LY3435151 and pembrolizumab.

The RP2D will be determined based on the number of observed dose-limiting toxicities (DLTs) and PK/pharmacodynamic (PD) data, and may be below the maximum tolerated dose (MTD), which may not necessarily be reached during the dose escalations. The dose-escalation phase will employ a modified toxicity probability interval (mTPI-2) method and starting with Cohort A2 will enroll at least three evaluable patients per cohort. Treatment cycles will consist of 21 days. A 2-cycle DLT observation will apply to all cohorts in Phase 1a. Refer to Section 4.1.1.1 for additional details on the dose escalation method.

A minimum of 1 patient will be enrolled in Cohort A1 and will receive a 10-mg dose. If the 10-mg dose level DLT period is cleared, Cohort A2 (30-mg dose level) will be initiated.

If a patient in Cohort A1 experiences a DLT, additional patients will be enrolled into Cohort A1 following the mTPI-2 method. Based on the mTPI-2 method, at least additional 4 patients will need to be enrolled and experience no DLT during the DLT observing period before escalating to the next dose level (Cohort A2).

After the first patient in Cohort A2 receives the first dose of LY3435151, there will be a delay of 1 week before the second patient receives LY3435151 to allow for safety observation. In all subsequent cohorts, the first patient in each dose level will be observed for at least 24 hours before treatment of additional patients; no additional delays are required for subsequent patients.

Patients in Cohorts A2, A3, A4, A5, and A6 will receive proposed doses of 30 mg, 100 mg, 300 mg, 900 mg, and 1800 mg, respectively, provided safety is established in the preceding cohorts. Once the DLT period of 42 days is completed for respective dose levels within Cohorts A1 to A6, 2 selected cohorts can be expanded with an additional 6 patients each to further inform safety, PK, and PD. For example, additional patients at dose level 5 (900 mg Q3W) may be enrolled in parallel with Cohort A6 after Cohort A5 has cleared the DLT period.

In the Combination Dose Escalation (Part B), 2 dose levels will be explored. Dose level 1 in Part B will be decided based on, but not limited to, the safety and PK/PD data from monotherapy expansion cohorts. The dose of pembrolizumab will remain constant. Once enrollment to dose level 1 in Part B begins, dose escalation will occur in parallel for both Part A and Part B. However, enrollment in a Part B cohort can begin only after all previous dose level cohorts in monotherapy and combination dose escalation (as applicable) are complete, as determined by Eli Lilly and Company (Lilly). For example, if dose level 5 900 mg Q3W is decided as the starting dose level for Part B, Cohort B1 will only begin after the safety of dose level 6 in monotherapy dose escalation is cleared, and Cohort B2 may begin only after both Cohort A6 and Cohort B1 are complete.

If safety data from Part A indicate that de-escalation of the LY3435151 dose is warranted, no additional patients will be enrolled in Treatment Part A or Treatment Part B at dose levels higher than the de-escalated dose.

Lilly and the investigators will hold a meeting to review safety and available PK/PD results after completion of the DLT period for each cohort to ensure it is safe to continue with the next dose-escalation cohort.

4.1.1.1. Dose Escalation Method

Dose escalation of LY3435151 will be driven by an mTPI-2 method taking into consideration available safety, PK, and PD data from previous dose levels for Cohorts A2 through A6. A minimum of 3 evaluable patients will be enrolled in Cohorts A2 through A6.

Similar to the 3+3 design, the mTPI-2 method incorporates prespecified escalation rules. However, the mTPI-2 method is based on quantitative models that incorporate uncertainty into the decision rules, thereby allowing more precise RP2D selection. If 3 or 6 patients are enrolled in a cohort, the escalation rule parallels a traditional 3+3 design. However, it allows flexible number of patients in a cohort. For example, with 2 DLTs per 6 patients enrolled, the mTPI-2 would recommend staying at the current dose, as analogy to 1 DLT per 3 patients enrolled in 3+3 design; therefore, it allows more patients for a more precise estimate of the DLT rate at this dose level.

Following a discussion between the Lilly clinical research physician/clinical research scientist (CRP/CRS) and the investigators, a more conservative dose selection may be applied to the next cohort (for instance, if PK/PD data suggest that further dose increase would not be expected to yield additional benefit). For example, if the rule indicates “E” to escalate, the dose may stay at the current dose level or be de-escalated to a lower level, or escalation may cease. In the mTPI-2, the cohort size is not fixed. However, each cohort from Cohort A2 through A6 will contain a minimum of 3 evaluable patients, unless the escalation rules dictate that the dose should be de-escalated (“D” or “DU”). Doses can be escalated, de-escalated, and re-escalated. If the dose

decision was “DU,” the dose cannot be re-escalated to that level. This study is designed to identify a dose level with a dose-limiting target toxicity rate of 30%. The mTPI-2 method considers an equivalence interval around the target toxicity rate. For this study, the equivalence interval is elicited to be (25%, 35%), indicating that any values between 25% and 35% can be considered as accepted toxicity rates for MTD. The final MTD will be the dose for which the estimated toxicity rate is the closest to the target toxicity rate of 30% and less than 35%. The resulting mTPI-2 decision rules for any cohort size up to 20, and a hypothetical example for DLT determination after all patients complete DLT evaluations, are provided in Appendix 6.

Safety data, in particular DLTs, will be the primary criteria for the dose escalation. In addition, if available at the time of dose escalation decision, PK/PD results (for example, maximum concentration [C_{max}], area under the concentration-time curve [AUC], PD results) will be used as secondary/supporting data for dose escalation.

Intermediate and/or higher dose schedules of administrations, as well as alternative schedules, will be explored if deemed necessary after discussion between Lilly and investigators and taking into account patient safety and PK/PD data. If needed, additional patients may be enrolled to further assess PK/PD or tolerability.

4.1.1.2. Dose-Limiting Toxicity Determination

A DLT is defined as any of the events listed in the table below if the event occurs during the DLT observation period (2 Cycles/42 days for Cohorts A1-A6 and B1-B2) in Phase 1a, and toxicity that is not clearly and directly related to the primary disease or another etiology.

Patients who experience a DLT in the DLT observation period will be discontinued from study treatment.

Dose-Limiting Toxicities of Study Treatment

Hematologic Toxicity

 • Grade 3 thrombocytopenia associated with clinically significant bleeding and /or requiring platelet transfusion or Grade 4 thrombocytopenia of any duration • Grade ≥ 3 febrile neutropenia and/or neutropenia requiring G-CSF • Grade ≥ 4 neutropenia lasting >7 days • Grade ≥ 3 anemia requiring a blood transfusion • Other Grade 4 toxicity lasting >7 days, excluding toxicities listed below and Grade 3 endocrine irAEs that can be managed by steroids or hormone replacement therapy
Nonhematologic Toxicity – Nonlaboratory

 • Grade 4 AE (unless stated otherwise below) • Any Grade ≥ 3 colitis or noninfectious pneumonitis irrespective of duration • Any other Grade 3 AE, excluding toxicities listed below • Grade ≥ 3 toxicity lasting >7 days despite optimal supportive care • Other Grade 2 irAE, excluding colitis or pneumonitis, that:

 ○ does not downgrade to Grade 1 within 3 days after onset of the event despite optimal medical management including corticosteroid therapy, or ○ does not downgrade to Grade 1 or the patient's baseline level within 14 days after onset of the event
Nonhematologic Toxicity – Laboratory/Investigations

 • Grade 3 or 4 laboratory value if: 
 ○ Medical intervention or hospitalization is required to treat the patient, or ○ The abnormality persists for >7 days (excluding amylase and lipase) • ALT or AST: 
 ○ >8 × ULN ○ ≥2-fold above the patient's baseline value that lasts >7 days, if the patient has HCC or liver metastasis and had ALT or AST >3.0 × ULN at baseline ○ ≥3 × ULN with concomitant bilirubin >2 × ULN, in the absence of cholestasis • Total bilirubin >3 × ULN • Grade ≥3 amylase or lipase that is associated with symptoms or clinical manifestations of pancreatitis
Other Hematologic or Nonhematologic Toxicity

 • Grade 5 toxicity (that is, death) • Grade ≥3 electrolyte abnormality that lasts >72 hours unless the patient has clinical symptoms, in which case all Grade ≥3 electrolyte abnormality regardless of duration should count as a DLT. • Treatment delay of >14 days due to an adverse event during Cycle 1 or Cycle 2. • Toxicity deemed by the investigator and Lilly CRP/CRS to be dose-limiting, such as toxicity that is possibly related to study treatment and requires discontinuation of the patient from the study at any time during Cycle 1 and 2.

Abbreviations: AE = adverse event; ALT = alanine aminotransferase; AST = aspartate aminotransferase; CRP/CRS = clinical research physician/clinical research scientist; DLT = dose-limiting toxicity; G-CSF = granulocyte colony-stimulating grown factor; HCC = hepatocellular carcinoma; irAE = immune-related adverse event; ULN = upper limit of normal.

Potential DLTs that are AEs that are reasonably anticipated AEs for concomitant medication should be reviewed by the treating investigator and Lilly CRP/CRS before final determination as a DLT. Review and discussion may include additional participating investigators. Such review may determine that confounding factors render the case to be not evaluable for the purposes of dose selection. Adverse events from such non-evaluable patients will also be reviewed throughout the dose escalation process in Phase 1a.

The definition excludes the following events:

- Toxicity that is clearly and directly related to the primary disease or to another etiology is excluded from this definition
 - Immune-related Grade 3 endocrine disorder (thyroid, pituitary, and/or adrenal insufficiency) that is managed with or without systemic corticosteroid therapy and/or hormone replacement therapy and the patient is asymptomatic

- Grade 3 inflammatory reaction attributed to a local antitumor response (such as inflammatory reaction in the lymph nodes or at sites of metastatic disease)
- Any grade vitiligo or alopecia
- First occurrence of Grade 3 infusion-related reaction (IRR) during infusion of LY3435151, if all of the following criteria are met:
 - the patient did not receive corticosteroid prophylaxis,
 - the Grade 3 IRR resolves within 6 hours with appropriate clinical management, and
 - if symptoms reappear, the event would be considered a DLT
- Grade 3 or 4 neutropenia meeting both of the following criteria:
 - is not associated with fever or systemic infection, and
 - improves by at least 1 grade within 7 days
- Grade 3 or 4 lymphopenia
- Grade 3 nausea or vomiting < 72 hours with adequate antiemetic and other supportive care
- Grade 3 fatigue < 1 week
- ≥ Grade 3 electrolyte abnormality that lasts <72 hours, is not clinically complicated, and resolves spontaneously or responds to conventional medical interventions
- ≥ Grade 3 amylase or lipase that is not associated with symptoms or clinical manifestations of pancreatitis

It should be recognized that, for patients who have received prior immune therapy, including checkpoint inhibitor therapy, there is the potential for delayed manifestation of serious immune-related adverse events (irAEs) such as colitis, hepatitis, pneumonitis, and endocrinopathies. Patients manifesting potential delayed irAEs should receive prompt evaluation and treatment.

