3. Have at least 1 measurable lesion assessable using standard techniques by Response Evaluation Criteria in Solid Tumors Version (RECIST) 1.1 (Eisenhauer et al. 2009). Use of positron emission tomography scans and ultrasounds for diagnostic purposes is not permitted.
 4. Are able and willing to provide the protocol required biopsies from a newly obtained core, endoscopic, or excisional pre-treatment biopsy of a tumor lesion and a newly obtained core, endoscopic, or excisional biopsy collected during the study treatment period (see Section 8.8).
 5. Have an Eastern Cooperative Oncology Group (ECOG) performance status of 0 or 1 (Oken et al. 1982).
 6. Have discontinued all previous treatments for cancer for at least 14 days and recovered from the acute effects of therapy. Patients must have discontinued from previous treatments, as shown below:

Previous Treatment	Length of Time Prior to First Dose of Study Treatment
Cytotoxic therapies or targeted agents that are small-molecule inhibitors	≥14 days
Mitomycin-C or nitrosoureas	≥42 days
Biologic agents (for example, antibodies such as anti-PD-1 or anti-PD-L1)	≥14 days
Radiotherapy	≥28 days if greater than 30% of bone marrow is irradiated or ≥7 days if less than 30% of bone marrow is irradiated. Participants must have recovered from all radiation-related toxicities, not require corticosteroids, and not have had radiation pneumonitis.
Limited field radiotherapy for palliative intent	≥14 days
Major surgery, excluding biopsy	Patients with recent major surgery must have recovered, in the opinion of the investigator, from the toxicity and/or complications from the intervention before starting therapy.

Abbreviations: PD-1 = programmed death-1; PD-L1 = programmed death-ligand 1.

7. For Phase 1a, prior anti-PD-1 or anti-PD-L1 therapy or other immunotherapy is allowed as long as the following criteria are met:

- a. did not experience a Grade 4 immune-related toxicity or any immune-related toxicity that led to permanent discontinuation of prior anti-PD-1, anti-PD-L1, or other immunotherapy
 - b. did not experience a less than or equal to Grade 3 irAE that has not recovered to Grade 1 after use of high-dose corticosteroids that occurred during prior immunotherapy
 - i. Patients with an endocrine AE are permitted to enroll if they are stably maintained on appropriate replacement therapy and are asymptomatic
 - c. did not experience any of the following irAEs during prior anti-PD-1, anti-PD-L1, or other immunotherapy:

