8.2.1. Clinical Safety Laboratory Assessments

- Lilly or its designee will provide the investigator with the results of safety laboratory tests analyzed by a central vendor, if a central vendor is used for the clinical trial.
- See Appendix 2 for the list of clinical laboratory tests to be performed and to the SoA (Section 1.3) for the timing and frequency.
- The investigator must review the laboratory report, document this review, and record any clinically relevant changes occurring during the study in the AE section of the CRF. The laboratory reports must be filed with the source documents. Clinically significant abnormal laboratory findings are those which are not associated with the underlying disease, unless judged by the investigator to be more severe than expected for the participant's condition.
- All laboratory tests with values considered clinically significantly abnormal during participation in the study or until the completion of Visit 801 after the last dose of study intervention should be repeated until the values return to normal or baseline or are no longer considered clinically significant by the investigator or medical monitor.
 - If such values do not return to normal/baseline within a period of time judged reasonable by the investigator, the etiology should be identified and the sponsor notified.
 - All protocol-required laboratory assessments, as defined in Appendix 2, must be conducted in accordance with the laboratory manual and the SoA (Section 1.3).

If there is an abnormal laboratory value or abnormal value for any other diagnostic or screening test (for example, blood pressure increased or neutrophils decreased) and it is known to be related to a disease diagnosis (for example, hypertension or neutropenia) this should be reported in the CRF as an AE. Do not enter the test abnormality, enter the disease diagnosis or categorical term. If laboratory values from non-protocol-specified laboratory assessments performed at the institution's local laboratory require a change in participant management or are considered clinically significant by the investigator (for example, SAE or AE or dose modification), then the event(s) must be reported in the CRF as AE(s).

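### A controlled, asymptomatic endocrine irAE still at Grade 2 after 14 days is a DLT, while the same disorder at Grade 3 is excluded

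*Protocol*

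**What the plan says.** All of the core text is in Protocol section 4.1.1.2.

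- **Trigger.** The nonlaboratory block of the DLT table lists "Other Grade 2 irAE, excluding colitis or pneumonitis, that" either fails to reach Grade 1 within 3 days despite optimal management, or fails to reach Grade 1 or the patient's "baseline level within 14 days after onset of the event". Colitis and pneumonitis are the only carve-outs in that row.
- **Exclusion.** The list after the table removes from the DLT definition an "Immune-related Grade 3 endocrine disorder (thyroid, pituitary, and/or adrenal insufficiency) that is managed with or without systemic corticosteroid therapy". Management may also be by replacing the hormone, and the exclusion applies only if there are no symptoms.
- **Consequence.** "Patients who experience a DLT in the DLT observation period will be discontinued from study treatment".

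Section 4.1.1.3 applies the same criteria outside the 42-day window in Phase 1a, and in every cycle of Phase 1b, as DLT-equivalent toxicities. Section 7.1 lists a DLT or a DLT-equivalent among the reasons for stopping the investigational product.

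The concern is limited to diagnosed disorders. For these, section 8.2.1 tells sites: "Do not enter the test abnormality, enter the disease diagnosis or categorical term".

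**The concern.** The endocrine exclusion recognises that a disorder controlled on replacement, without symptoms, should not limit the dose. It then stops at Grade 3. A controlled Grade 2 disorder falls back under the persistence rule, which considers neither symptoms nor replacement therapy.

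Nothing suggests that this was intended. Where the list means all grades it says so, as for vitiligo and alopecia. Elsewhere the protocol accepts controlled endocrine events above Grade 1:

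- Inclusion criterion 7b requires that a patient "did not experience a less than or equal to Grade 3 irAE that has not recovered to Grade 1 after use of high-dose corticosteroids", but exempts asymptomatic endocrine events on stable replacement, with no grade limit.
- The irAE table in section 6.6.1 says to continue treatment for Grade 2 hyperthyroidism and for Grade 2 to 4 hypothyroidism.
- Footnote d of that table, attached to new-onset diabetes or hyperglycaemia, hypophysitis and hyperthyroidism, allows treatment to resume at Grade 2 or below. The general irAE instruction requires Grade 1 or below.

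DLTs are a primary Phase 1a endpoint and the main input to dose escalation. A misclassified event can hold or lower the dose and remove a patient who is tolerating treatment. In Phase 1b, a site treating Grade 2 hypothyroidism controlled on replacement would read *continue* in section 6.6.1 and *discontinue* in section 7.1.

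**Working it through.** **1. The two grades side by side (section 4.1.1.2).** Take a diagnosed, managed, asymptomatic endocrine irAE that remains at its grade for 14 days.

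| Grade | Trigger | Covered by the endocrine exclusion? | Result |
|---|---|---|---|
| 2 | Grade 2 irAE row, 14-day limb (possibly the 3-day limb sooner) | No, Grade 3 only | DLT |
| 3 | Other Grade 3 AE; Grade 3 or higher lasting over 7 days | Yes | Not a DLT, unless another criterion applies |

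No other listed exclusion covers the Grade 2 case. The joint review of potential DLTs concerns events anticipated for concomitant medication, so it is not an endocrine exception. The only other mention of endocrine irAEs in the table, in the hematologic block, is also at Grade 3.

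**2. Can it happen inside the window?** The scheduled on-treatment thyroid test is at Cycle 2 Day 1, which is study Day 22. If onset is dated then, the 14-day limit falls at 22 + 14 = Day 36, within the 42 days.

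**3. Effect on mTPI-2.** Inputs from section 4.1.1.1: target 0.30, equivalence interval (0.25, 0.35). Assumptions: Beta(1,1) prior, subintervals of width 0.10 (truncated at 0 and 1), and DU when P(p > 0.30) exceeds 0.95. With x DLTs in n patients the posterior is Beta(1 + x, 1 + n − x). The decision follows the interval with the largest posterior probability divided by its width.

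Check against every cell the protocol states:

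| DLTs / patients | Protocol | Rebuilt |
|---|---|---|
| 1/3 | S (Appendix 6) | S |
| 2/3 | D (Appendix 6) | D |
| 1/6 | E (Appendix 6) | E |
| 5/7 | DU (Appendix 6) | DU |
| 2/6 | stay (section 4.1.1.1) | S |
| 1/5 | E (section 4.1.1: one DLT plus four clean patients) | E |

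Effect of counting one additional endocrine event as a DLT:

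| Without it | With it | Change |
|---|---|---|
| 0/3 E | 1/3 S | escalate to stay |
| 0/4 E | 1/4 S | escalate to stay |
| 0/5 E | 1/5 E | none |
| 0/6 E | 1/6 E | none |
| 1/3 S | 2/3 D | stay to de-escalate |
| 1/4 S | 2/4 D | stay to de-escalate |
| 1/5 E | 2/5 D | escalate to de-escalate |
| 1/6 E | 2/6 S | escalate to stay |

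If Cohort A1 has a single patient, one such event means at least four more DLT-free patients before Cohort A2 opens (section 4.1.1). After 1/3, two more clean patients give 1/5 and restore escalation, each needing 42 days of follow-up. A de-escalation in Part A closes higher doses in both Parts A and B.

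**4. Frequency.** The documents give none. If 5%, 10% or 20% of patients had such an event within 42 days (assumed values), the chance of at least one in a cohort of 3 is 1 − (1 − q)³ = 14%, 27% or 49%.

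**5. Phase 1b patients subject to the rule.** 2 × 16 + 2 × 32 + 30 = 126. Of these, 2 × 8 + 2 × 32 + 30 = 110 receive the combination and 2 × 8 = 16 monotherapy. This counts the patients to whom the rule applies; it is not an effect size.

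**The case against.** The literal reading is hard to dispute. The case on the other side concerns how much it matters.

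- **The contrast is narrower for some disorders.** Grade 3 hypophysitis and hyperthyroidism are withhold or discontinue in section 6.6.1, and "Treatment delay of >14 days due to an adverse event during Cycle 1 or Cycle 2" is a separate DLT. Some excluded Grade 3 events would therefore still count by that route. This stands; the contrast is cleanest for hypothyroidism.
- **Detection is limited.** Only one on-treatment thyroid test is scheduled in the 42-day window, and Appendix 2 lists no routine pituitary or adrenal hormone test. Many cases would need unscheduled testing or earlier symptoms. This also stands.
- **The Phase 1b conflict is partly a general one.** Section 4.1.1.3 allows dose modification after any DLT-equivalent, while section 7.1 requires discontinuation. If section 4.1.1.3 governs, the patient with controlled hypothyroidism continues. Dose re-evaluation is tied to a 30% cumulative DLT-equivalent incidence.
- **The supporting passages are not DLT standards.** Criterion 7b concerns earlier therapy. Section 6.6.1 also says continue for Grade 4 hypothyroidism, although a Grade 4 AE is generally a DLT. Grade 2 hypophysitis and other persistent Grade 2 irAEs are withhold there, so no conflict arises for them.
- **The direction is cautious and buffered.** Re-escalation is allowed unless the decision was DU, the RP2D rests on the totality of data, and a strict Grade 2 rule may be deliberate.

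These points reduce the expected impact. None explains why a controlled Grade 2 disorder should count when the same disorder at Grade 3 does not.

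**Conclusion.** The concern holds: the DLT definition reverses the order of severity for controlled, asymptomatic endocrine irAEs. It should be fixed because it affects a primary Phase 1a endpoint, the escalation decision and whether a patient stays on treatment. It is not a safety hazard, since the error only adds DLTs and discontinuations.

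The reading of the text needs no statistical assumption. The mTPI-2 effects rest on the assumed prior, subintervals and DU cutoff, which together reproduce all six decisions the protocol states. The practical frequency is unknown. It depends on how CTCAE v5.0, which the documents cite but do not reproduce, grades a treated event, and on how often sites test. The direct conflict with section 6.6.1 is claimed for thyroid events only.

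**What to change.** In the endocrine exclusion of section 4.1.1.2, replace *Grade 3* with *Grade 2 or Grade 3* and keep the conditions that the disorder is managed and the patient asymptomatic. A cross-reference in the Grade 2 irAE row would help sites but is optional. Section 4.1.1.3 needs no edit, because it takes the DLT criteria as already defined.

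What stays a DLT: symptomatic Grade 2 events past the time limits, symptomatic Grade 3 events, Grade 4 events, and treatment delays over 14 days in Cycle 1 or 2.

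What the change leaves open: it removes the conflict with section 6.6.1 only for asymptomatic Grade 2 thyroid events. Symptomatic and Grade 4 thyroid events would still differ from *continue* where that applies, and the general mismatch between sections 4.1.1.3 and 7.1 remains.

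Cost: one phrase. Slightly fewer events count as DLTs, so escalation becomes slightly less conservative. The Appendix 8 history records that the DLT table was modified on FDA feedback, without saying which rows, so the change needs clinical and possibly regulatory sign-off.
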